The demographics of patients with cystic fibrosis have shifted, and this shift has important implications for antimicrobial therapy. Once considered primarily a childhood disease, improvements in care have substantially increased the proportion of CF patients surviving into adulthood. In 1986, 70.8% of patients with CF were under 18 years of age. Data from 2016 CF Foundation Patient Registry Annual report show that the majority of patients currently living with CF are adults (52.7%) and that median survival is now well into middle age (47.7 years).¹ The prevalence of positive cultures for MDR *P. aeruginosa* is less than 10% in pediatric patients with CF, but increases steadily to around 20% in adults age 30-40 years.¹ This increase in drug-resistance over time likely reflects recurrent exposure to antipseudomonal antibiotics resulting in a severely limited armamentarium of active antibiotics to treat these patients into adulthood.

The polymyxins are cyclic peptide antibiotics which are positively charged at physiologic pH and exert bactericidal activity through binding to the lipopolysaccharide component of gram-negative bacterial membranes.³ Colistin, which is commercially available as the prodrug colistimethate sodium, has historically been the most commonly used polymyxin in patients with and without CF.^{4,5} There has been renewed interest into these compounds in the patients without CF due to the epidemic of antibiotic resistance. Population PK studies in critically ill patients have demonstrated high inter-patient variability in the exposure of formed colistin and inadequate attainment of therapeutic levels in patients with adequate or augmented renal function.^{6,7} The variability between patients in colistin exposure is due to variable conversion from colistimethate, which requires removal of five pro-drug functional groups, as

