well as the differential pathways of elimination for colistimethate and formed colistin. Colistimethate is freely filtered and excreted in urine whereas formed colistin is avidly reabsorbed in the kidney and eliminated by non-renal mechanisms.⁸ The renal elimination of the inactive prodrug before conversion to the pharmacologically active form makes achieving colistin exposures associated with effective bacterial killing challenging in patients with adequate renal function. Patients with CF generally exhibit augmented clearance of renally eliminated compounds placing them at increased risk for underexposure.⁹ Polymyxin B, which is administered directly as active drug and reabsorbed in the kidney in a manner analogous to formed colistin, has demonstrated more consistent PK in critically ill patients.¹⁰⁻¹²

The impact of patient-specific variables on the PK of the polymyxins has been an area of active investigation. As highlighted above, patient renal function has a significant bearing on the PK of colistin, through its prodrug colistimethate sodium, but has negligible impact on polymyxin B.¹⁰⁻¹² Therefore, despite the fact that the polymyxin B label includes renal dose adjustments, this agent is dosed without respect to patient renal function in clinical practice.¹³ The only PK study of polymyxin B in patients with CF included 9 patients with only a median of 2 samples analyzed per patient (31 samples total).¹⁴ Interestingly, this study did identify a relationship between polymyxin B CL and creatinine clearance; however, the validity and magnitude of this relationship are uncertain given that most of the observed effect was due to a single patient. The other patient-specific factor which has traditionally informed the dosing of these agents is patient body weight. Population PK studies of colistin from the modern era of use have challenged the traditionally held belief that the clearance and volume of distribution scale with patient weight.^{6,7} In fact, the updated European Medicines Agency labeling for colistin recommends fixed-doses stratified by patient renal function based on these data.¹⁵ Similarly, the most recent PK studies of polymyxin B have failed to demonstrate an impact of patient body weight on the clearance of polymyxin B; however, the majority of polymyxin B dosing in clinical practice is still weight-based.^{11,12}

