6.1. Population Pharmacokinetic Analysis

6.1.1. Pharmacokinetic Modeling: The PK data will be analyzed using a population PK modeling approach through the nonparametric adaptive grid (NPAG) algorithm in the Pmetrics™ package for the R environment.^{21,22} Models will be parameterized as one- and two-compartment systems with zero-order infusion and elimination from the central compartment modeled as a first-order process. Michaelis-Menten and mixed-order linear/Michaelis-Menten elimination will be tested if first-order processes alone do not display adequate fit of the data.

For all models, the inverse of the estimated assay variance will be used as the first estimate for weighting. Weighting will be accomplished by making the assumption that total observation variance is proportional to assay variance. Assay variance will be determined on a between-day basis. The analysis will be performed with adaptive γ , a scalar which is optimized with each cycle to produce the best approximation to the homoscedastic assumption.

Models will be run for at least 100 cycles and Bayesian estimates will be obtained for each patient. For each model, both the mean and median will be employed as measures of central tendency for the population parameter estimates and will be evaluated in the Bayesian analysis. Scatter plots will be examined for individual patients and for the population as a whole.

6.1.2. Monte Carlo Simulation: The parameter vector and covariance matrix from population PK modeling will be used as the prior distribution for the simulation function within Pmetrics™. 1000-subject Monte Carlo simulations will be performed for candidate dosing regimens.

The simulated plasma concentration-time curves will be used to calculate area under the concentration-time curve (AUC) values for different 24-hour increments through 96 hours. For each regimen examined, probability of efficacy will be the fraction of the simulated subjects at each time interval for which the 24-hour AUC is between 50 – 100 mg*h/L while the probability of toxicity will be the fraction of subjects with 24-hour AUC values ≥ 100 mg*h/L.^{23,24}

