6.3. Statistical Analysis

6.3.1. Baseline demographic and clinical data: Baseline demographic and clinical data will be assessed using descriptive statistics. Variables will be summarized as mean (standard deviation), median (5th, 95th percentile), or number (percentage) as indicated.

6.3.2. Population pharmacokinetic analysis: Model goodness-of-fit of the observed data will be assessed by regression with an observed-predicted plot. Between-subject variability will be quantified using coefficients of determination. Model discrimination will be based on log-likelihood (-2LL) and Akaike's Information Criterion (AIC) objective function values as well as diagnostic plots. Predictive performance evaluation will be based on weighted mean bias and the bias-adjusted weighted mean precision.

6.3.3. Toxicity analysis: Nephrotoxicity and neurotoxicity rates will be summarized as number (percentage). Time to renal recovery will be summarized as mean (standard deviation) or median (interquartile range) days as indicated while renal recovery by hospital discharge will be summarized as number (percentage).

7. Benefits and Risks

7.1. Benefits:

7.1.1. Current CF Foundation guidelines recommend that two antibiotics with activity against *P. aeruginosa* as the standard of care for treatment of acute pulmonary exacerbations. Many adult CF patients have had extensive lifetime exposure to antipseudomonal antibiotic therapy and may require therapy with last line agents due to multi-drug resistance in clinical isolates. The polymyxins, colistin and polymyxin B, are often required as combination salvage therapy for isolates with documented resistance to aminoglycosides or fluoroquinolones. Polymyxin B has significant pharmacokinetic advantages to colistin for CF patients; however, limited data exist in this patient subpopulation to guide dosing in practice. The data generated by this study will be used to confirm dosing of polymyxin B in this population and ensure safety with commonly administered doses extrapolated from non-CF patient populations. There is no direct benefit to patients enrolled in the study at the time of enrollment; however, patients treated with polymyxin B at the time of the study are at risk for re-infection with MDR organisms in the future. Therefore, PK data obtained in this study could inform the dosing of polymyxin B for the treatment of future infections with MDR organisms.

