10.1. Appendix I: Laboratory Protocol

Laboratory Protocol

1. Blood Collection Tubes

Plastic Lavender Top K2-EDTA Tube (BD, Franklin Lakes, NJ, Catalog# 367863)

2. Blood Collection Supply Quantities

Five blood samples are to be obtained and processed per subject on polymyxin B therapy. Samples will be collected at the time points listed below relative to the end of polymyxin B infusion (t_{inf})

Sample Code	Collection Timepoint	Collection Time Relative to Duration of Infusion (t_{inf})
C_0	Prior to Start of Infusion	0 hour
C_1	End of Infusion	$t_{inf} + 0$ hour
C_2	One Hour after End of Infusion	$t_{inf} + 1$ hour
C_3	Three Hours after End of Infusion	$t_{inf} + 3$ hours
C_4	Eight Hours	8 hours

Minimum Supplies Necessary:

Up to 20 subjects \times 5 blood collection tubes = 100 Blood Collection Tubes
 100 blood samples \times 2 plasma aliquots/blood sample= 200 cryovials (Screw Capped Polypropylene, 1-2 mL)
 200 cryovials \times 1box/81 cryovials= 3 cryovial storage boxes

3. Pre-Study Preparation

a. Plasma collection tubes

- i. Label 5 plasma collection tubes per subject with:
 - 1) study protocol number
 - 2) the study subject code
 - a) color code with a highlighter pen (yellow, pink, green, orange) the subject code if more than one subject is to be studied on the same date
 - 3) date of collection

- 4) sample code (i.e. C₀, C₁, etc.)
 - ii. Transfer plasma collection tubes to a test-tube rack
 - 1) Individual test-tube racks should be used for each subject if more than one subject is to be studied on the same day
 - iii. Pre-chill (2-8°C) plasma collection tubes prior to blood collection
 - b. Cryovials
 - i. Label 10 cryovials per subject with:
 - 1) study protocol number
 - 2) the study subject code
 - a) color code with a highlighter pen (yellow, pink, green, orange) the subject code if more than one subject is to be studied on the same date
 - b) the color code should match the plasma collection tube for each subject to reduce the risk of potential transfer error
 - 3) date of collection
 - 4) sample code (i.e. C₀, C₁, etc.)
 - 5) aliquot number (AQ-1, AQ-2)
 - ii. Transfer cryovials to a rack
 - 1) Individual cryovial racks should be used for each subject if more than one subject is to be studied on the same day
 - c. Cryovial boxes
 - i. Label 2 cryovial boxes with:
 - 1) study protocol number
 - 2) date of collection
 - 3) aliquot number (AQ-1 and AQ-2)

4. Blood Sample Collection and Processing

- a. Collection

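### Section 6.3.2 measures between-subject variability by R-squared, and no section names a valid measure of spread for clearance or volume

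*Combined protocol and SAP*

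**What the plan says.** In section 6.3.2 the rule is: "Between-subject variability will be quantified using coefficients of determination". The sentence just before it deals with model fit: "Model goodness-of-fit of the observed data will be assessed by regression with an observed-predicted plot". It does not say whether the predictions are population or individual (Bayesian) predictions.

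Other parts of the plan bear on the same quantity:

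- Section 6.1.1 estimates individual values ("Bayesian estimates will be obtained for each patient"). For summarising the population parameters it names only the centre: "both the mean and median will be employed as measures of central tendency for the population parameter estimates".
- Section 6.1.2 carries the estimated spread into simulation: "The parameter vector and covariance matrix from population PK modeling will be used as the prior distribution". It then reports, for each regimen, the fraction of simulated subjects with a 24-hour AUC of 50 to 100 mg*h/L and the fraction at or above 100 mg*h/L.
- Section 6.3.1 gives SDs and percentiles, but for baseline demographic and clinical data. Section 6.3.3 gives an SD or interquartile range, but for time to renal recovery.

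**The concern.** The statistic named for between-subject variability answers a different question. R-squared is the share of variation in observed concentrations that predictions account for. It gives one number per plot, so it cannot provide separate figures for clearance (CL) and volume (V). It does respond to between-subject spread, but also to residual error, to the sampling times and to the choice of prediction.

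Variability is part of the study's rationale. The Background (section 3) reports "high inter-patient variability in the exposure of formed colistin" and says that polymyxin B "has demonstrated more consistent PK in critically ill patients". Aim 4.2 is to characterise the drug's PK in adults with CF. A reader of the results would want to know how much CL and V vary in this population. Followed literally, the plan would put an R-squared under that label, and it could not be set beside a CV from another study.

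**Working it through.** **Step 1: is a valid measure named elsewhere?** The plan has no figure here to reproduce, so the first check is of the text. The candidates are the mean and median in 6.1.1 (centre only), the covariance matrix in 6.1.2 (named as a simulation input), the AUC fractions in 6.1.2 (spread in exposure, shown indirectly), the weighted bias and precision in 6.3.2 (prediction error), and the summaries in 6.3.1 and 6.3.3 (other variables). None assigns an SD, variance, CV or percentile range to CL or V.

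**Step 2: could R-squared stand in for a CV?** This was tested by simulation.

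Inputs from the document:
- 20 subjects, the ceiling in Appendix 10.1 ("Up to 20 subjects").
- 5 samples each at the Table 1 times. With a 1 h infusion these are pre-dose, 1, 2, 4 and 8 h.
- 100 mg every 12 h, the maintenance dose listed in 5.6.2 for patients above 50 kg, at steady state.

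Assumptions not in the document:
- One compartment, CL 2.5 L/h, V 35 L, 1 h infusion.
- Independent lognormal variation in CL and V, with log-scale SD s = sqrt(ln(1 + CV²)).
- Proportional residual error of 5%, 15% or 30%.

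Formulas:
- With k = CL/V, infusion rate R = 100 mg/h, infusion time 1 h and interval 12 h, the concentration after the infusion is C(t) = (R/CL) × (1 − e^(−k·1)) × e^(−k(t−1)) / (1 − e^(−12k)).
- The pre-dose sample is the same expression at t = 12.
- R-squared is the squared correlation between observed and predicted concentrations.

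Mean R-squared at true CV 10% / 30% / 60%:

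| Residual error | True individual curve | Bayesian (MAP) prediction | Population prediction |
|---|---|---|---|
| 5% | 0.97 / 0.98 / 0.99 | 0.98 / 0.99 / 0.99 | 0.86 / 0.49 / 0.22 |
| 15% | 0.77 / 0.85 / 0.92 | 0.80 / 0.89 / 0.94 | 0.69 / 0.42 / 0.20 |
| 30% | 0.46 / 0.59 / 0.74 | 0.49 / 0.65 / 0.79 | 0.41 / 0.30 / 0.16 |

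The true-curve and population columns are means of 2000 replicates. The MAP column uses 60 replicates with the true typical values and variances as prior, and its figures are good to about 0.02.

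Reading the table:
- *Insensitive where data are good.* At 5% error, a sixfold rise in CV moves the true-curve R-squared by 0.99 − 0.97 = 0.02.
- *Driven by noise.* At a fixed CV of 10%, residual error alone moves it by 0.97 − 0.46 = 0.51.
- *Direction not fixed.* As CV rises, R-squared rises against individual predictions and falls against population predictions.
- *Not invertible.* A population R-squared of 0.41 to 0.42 arises from CV 30% with 15% error and from CV 10% with 30% error.

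With V at 30 L and infusions of 1 h or 2 h the pattern is the same. In those runs the median sample CV of the simulated CL values was 10%, 28–29% and 53–55% for true CVs of 10%, 30% and 60%. It did not depend on residual error, because it was taken from the simulated parameters themselves.

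**Step 3: how precise would a correct CV be with 20 subjects?** Take an observed CV of 30% and suppose each patient's parameter is known exactly.
- s = sqrt(ln 1.09) = 0.294.
- With 19 degrees of freedom the 95% multipliers are sqrt(19/32.85) = 0.76 and sqrt(19/8.91) = 1.46, giving log-scale limits of 0.223 and 0.429.
- Converting back, sqrt(e^(0.223²) − 1) = 22.6% and sqrt(e^(0.429²) − 1) = 44.9%.

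This does not bear on the error itself. It only shows why an interval would be useful.

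**The case against.** The strongest reply is that this is a slip of wording. One word separates determination from variation, and R-squared would be at home in the preceding sentence. Nothing operative depends on it: models are chosen on -2LL, AIC and diagnostic plots, and the simulation uses the covariance matrix. The diagonal of that matrix holds the between-subject variances, so a CV follows by arithmetic from planned output. No comparison with a CV from other studies is planned, Aim 4.2 sets no variability target, and the AUC fractions already convey spread in exposure. The simulation rests on assumed values and illustrates what is true by definition.

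Much of this stands. The spread will be estimated, the error can be repaired from planned output, and the effect is confined to one reported result. The interval is an improvement and is not needed to cure the defect. But the document does not say that variation was meant, and this is the sentence that governs the analysis. A probable slip there still needs correcting. That the right figure can be extracted does not make the named one right.

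**Conclusion.** The point holds as a should-fix. Section 6.3.2 assigns the wrong statistic to between-subject variability, and no other section assigns a right one to CL or V. That conclusion rests on the text and on the definition of R-squared. The simulated values rest on the assumed PK parameters, error model and residual error range; they show how badly the substitute behaves and do not predict this study's results. Model fitting, model choice, dosing simulation and toxicity summaries are untouched. What would be wrong is the number reported as between-subject variability.

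**What to change.** Replace the sentence in 6.3.2 with: *Between-subject variability in each PK parameter will be quantified as CV%, with SD or percentiles of the nonparametric distribution, from the weighted NPAG support points, with an interval for its uncertainty.* Keep coefficients of determination only for the observed-predicted regression, and state there whether population or individual predictions are used.

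The cost is a one-sentence replacement and that short clarification. CV, SD and percentiles come from the NPAG output already planned. The interval is the only added work, for example a bootstrap over subjects. If the sponsor prefers to keep the report purely descriptive, the interval can be dropped and the correction is still complete.

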The polymyxins are associated with significant toxicities, namely, nephrotoxicity and neurotoxicity, which limit their clinical use. Therefore, it is important to assess the relative toxicity of colistin and PMB to ensure that shifting use to PMB for its PK advantages does not lead to increased toxicity. The comparative nephrotoxic potential of colistin and polymyxin B has been extensively investigated in non-CF populations, primarily the critically ill, and a meta-analysis of recent observational studies found an increased risk for acute kidney injury (AKI) with colistin relative to polymyxin B (RR 1.55, 95% CI 1.36-1.78).¹⁶ Only two studies assessing nephrotoxicity of both colistin and polymyxin B have included patients with CF. Phe and colleagues included 38 patients with CF and found that CF was actually protective against colistin associated AKI (aOR 0.03, 95% CI 0.001-0.79) in multivariable analysis.¹⁷ Unfortunately, no CF patients in this study received polymyxin B, so the relative rates of kidney injury between the two agents in this population could not be assessed. A 2017 study investigated the association between polymyxin treatment and kidney injury in 220 adult CF patients, 29 treated with PMB and 191 treated with colistin.¹⁸ The study found no difference in rates of AKI between PMB and colistin (34.5% vs 29.8%, p = 0.77) in patients nor in the rates of renal recovery by hospital discharge (90.0% vs 91.2%, p = 1.00). Neurotoxicity with the polymyxins are poorly characterized in patients with and without CF, especially with polymyxin B. Studies with colistin in pediatric patients with CF have found rates of neurotoxicity between 0 – 97.3% with many demonstrating higher rates of neurotoxicities than AKI.⁵ The most common manifestation of neurotoxicity with polymyxins is mild-moderate perioral paresthesia followed by weakness, ataxia, and in rare cases respiratory compromise.^{5,19,20} Neurotoxicity has not been evaluated in studies comparing colistin and PMB.

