5.6. Dosing and Administration

5.6.1. The dose and duration of infusion for PMB will be determined at the discretion of the prescribing physician in the course of routine clinical care. There is no study intervention on the dosing and administration of PMB.

5.6.2. The recommended dosing schedule for intravenous polymyxin B at Michigan Medicine consists of an initial weight-based loading dose (2 mg/kg, maximum of 200 mg) followed by 100 mg every 12 hours for the duration of therapy as determined by the clinician. A reduction of the maintenance dose to 75 mg every 12 hours is recommended for patients with total body weight less than or equal to 50 kg.

5.7. Sampling:

5.7.1. Blood samples will be collected from enrolled patients at 5 time points during a single dosing interval under steady-state conditions. Sampling will occur on any day of therapy immediately prior to and following a single dose of PMB. The infusion time is selected at the discretion of the prescribing physician; thus the sampling schema is described based on the duration of infusion (Table 1).

Table 1: Sample collection times

Sample Code	Collection Timepoint	Collection Time Relative to Duration of Infusion (t_{inf})
C_0	Prior to Start of Infusion	0 hour
C_1	End of Infusion	$t_{inf} + 0$ hour
C_2	One Hour after End of Infusion	$t_{inf} + 1$ hour
C_3	Three Hours after End of Infusion	$t_{inf} + 3$ hours
C_4	Eight Hours	8 hours

5.7.2. Blood samples will be collected via one of three sampling methodologies: peripheral venipuncture, peripheral intravenous catheter, or a central venous catheter (e.g., PICC, Port). The method of obtaining blood samples will be determined by study personnel and will consider patient preference, patient safety, and the likelihood of obtaining adequate samples. Insertion of, care for, and sampling from indwelling catheters will be performed per hospital policy.

5.7.3. The procedure for obtaining and processing blood samples can be found in the Laboratory Protocol document in the Appendix (10.1).

5.8. Demographic and Clinical data: Study team members will obtain demographic and clinic data needed to describe the study population and build pharmacokinetic models. Data will be abstracted from DataDirect or obtained directly from the medical record for each index encounter. Data recorded directly from the medical record will be stored in REDcap.

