6.2. Toxicity Analysis

6.2.1. Nephrotoxicity: Nephrotoxicity will be assessed using the KDIGO criteria to define AKI. The nephrotoxicity endpoint will be met if subjects meet criteria for any stage of AKI by the KDIGO criteria using measured serum creatinine (Table 2). The degree of AKI will also be described by KDIGO stage. Time to renal recovery after cessation of PMB and the proportion of patients with renal recovery by hospital discharge will also be assessed. Renal recovery is defined as resolution of all KDIGO criteria for AKI.

Table 2: Definition of AKI using the KDIGO criteria

Stage	Serum Creatinine
1	1.5 – 1.9 x baseline OR ≥ 0.3 mg/dL increase from baseline
2	2.0 – 2.9 x baseline
3	≥ 3.0 x baseline OR

	$\geq 4 \text{ mg/dL}$ OR Initiation of renal replacement therapy
--	--

6.2.2. Neurotoxicity: Neurotoxicities will be assessed by patient self-report. The type of toxicity, anatomic site of toxicity, and severity will be assessed by the study personnel using the National Cancer Institute: Common Terminology Criteria for Adverse Events (NCI:CTCAE) scale.²⁵

Table 3: NCI:CTCAE terminology and definitions for potential neurotoxicities

CTCAE Term	Definition
Apnea	A disorder characterized by cessation of breathing
Ataxia	A disorder characterized by lack of coordination of muscle movements resulting in the impairment or inability to perform voluntary activities
Confusion	A disorder characterized by a lack of clear and orderly thought and behavior
Dizziness	A disorder characterized by a disturbing sensation of lightheadedness, unsteadiness, giddiness, spinning, or rocking
Dyspnea	A disorder characterized by an uncomfortable sensation of difficulty breathing
Hallucinations	A disorder characterized by a false sensory perception in the absence of an external stimulus
Hearing impairment	A disorder characterized by partial or complete loss of the ability to detect or understand sounds resulting from damage to ear structures
Muscle Weakness	A disorder characterized by a reduction in the strength of muscles in multiple anatomic sites
Paresthesia	A disorder characterized by functional disturbances of sensory neurons resulting in abnormal cutaneous sensations of tingling, numbness, pressure, cold, and/or warmth
Peripheral motor neuropathy	A disorder characterized by damage or dysfunction of peripheral motor nerves
Peripheral sensory neuropathy	A disorder characterized by damage or dysfunction of peripheral sensory nerves

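### Section 6.3.3 does not say how patients with unrecovered AKI enter the time to renal recovery; a mean or median over recovered patients alone understates it for AKI present at or after polymyxin B cessation

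*Combined protocol and SAP*

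**What the plan says.** Section 6.2.1 names two recovery outputs: "Time to renal recovery after cessation of PMB and the proportion of patients with renal recovery by hospital discharge". It defines the event: "Renal recovery is defined as resolution of all KDIGO criteria for AKI". For the first output, section 6.3.3 plans: "Time to renal recovery will be summarized as mean (standard deviation) or median (interquartile range) days", with the choice between the two left open. The second output is a number and percentage.

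The AKI and neurotoxicity outcomes are treated the same way: "Nephrotoxicity and neurotoxicity rates will be summarized as number (percentage", with no confidence interval.

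Treatment length is not fixed. The recommended schedule in section 5.6.2 runs "for the duration of therapy as determined by the clinician". AKI can therefore resolve on PMB, persist past cessation, or begin after it.

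Section 5.8 ties data abstraction to the index encounter. Figure 1, whose legend lists serum creatinine, is not shown, and section 5.8.8 collects readmission, so some creatinine values after discharge may exist. The readable text gives no rule for a patient who is unrecovered at the last creatinine or who dies unrecovered, and names no method for censored times.

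**The concern.** By reporting the proportion recovered by discharge, the plan accepts that some patients may not recover in the period observed. Those patients cannot contribute a recovery time to an average. If the average is taken over the rest, it describes the patients who recovered within the observed window, but it would be printed without that label and read as the recovery time after PMB stops.

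Safety is one of three stated aims (4.3), and section 7.1.1 says the data will "ensure safety with commonly administered doses extrapolated from non-CF patient populations". With about seven AKI cases expected, one or two unrecovered patients can move the reported time. Bare percentages from so few subjects also hide how little they rule out.

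**Working it through.** **Inputs.** Section 3 cites a study of adult CF patients, "29 treated with PMB and 191 treated with colistin", with AKI in 34.5% and 29.8% (p = 0.77), and recovery by discharge in 90.0% and 91.2% (p = 1.00). The only cohort size is the laboratory supply count in Appendix I, up to 20. The documents give no recovery times or discharge days, so those are assumed below.

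**The cited figures reproduce.** Back-calculated counts are 10/29 = 34.5%, 57/191 = 29.8%, 9/10 = 90.0% and 52/57 = 91.2%. Chi-square with continuity correction gives p = 0.77 for AKI. Fisher's exact test gives p = 1.00 for recovery.

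**Chance of an unrecovered patient.** Expected AKI cases: 20 × 0.345 = 6.9. Expected unrecovered: 6.9 × 0.10 = 0.69.

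P(at least one) = 1 − (1 − AKI × (1 − recovery))^n = 1 − (1 − 0.0345)^20 = 50%.

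P(two or more) = 50.4% − 20 × 0.0345 × 0.9655^19 = 15%.

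| Case | P(at least one) |
|---|---|
| Both drugs combined, 67/220 AKI and 61/67 recovered, n = 20 | 42% |
| AKI 34.5%, recovery 95%, n = 20 | 29% |
| AKI 34.5%, recovery 80%, n = 20 | 76% |
| AKI 17.9%, recovery 95%, n = 20 | 16% |
| AKI 54.3%, recovery 80%, n = 20 | 90% |
| Cited PMB rates, n = 15 | 41% |
| Cited PMB rates, n = 10 | 30% |

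The AKI limits 17.9% and 54.3% are the exact 95% interval for 10/29.

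**Shortfall of a recovered-only summary.** Assume exponential recovery from cessation, the same discharge day for all, and a fraction q recovered by then.

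- Mean: shortfall = (1 − q) × (−ln(1 − q)) / q. At q = 0.9: 0.1 × 2.303 / 0.9 = 25.6%.
- Median: shortfall = 1 + ln(1 − q/2) / ln 2. At q = 0.9: 1 − 0.598/0.693 = 13.8%.
- At q = 0.8: 40.2% and 26.3%. At q = 0.95: 15.8% and 7.0%.
- If discharge days vary independently of recovery (q = 0.9; exponential or gamma discharge times): mean 10.0 to 19.5%, median 10.0 to 13.6%.

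Entering the discharge day as if it were a recovery time does not rescue the mean. With discharge fixed at day 7 and 90% recovered, a true mean of 3.0 days is reported as 2.7.

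**In days.** Assume seven AKI cases and 90% recovery by an assumed discharge on day 10. Average medians by simulation, recovered-only against unrecovered ranked last:

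- one unrecovered: 2.8 against 3.4;
- two unrecovered: 2.8 against 4.4.

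**Which population.** These comparisons hold for AKI present at or after cessation. Patients whose AKI resolved on PMB have no positive time from cessation. If they are counted as day 0 (a convention the plan does not state) and one of the seven is unrecovered, then:

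- with one resolved on PMB, the recovered-only and all-AKI medians are equal (2.8 and 2.8);
- with two, the recovered-only median is longer (2.9 against 2.1).

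**Exact (Clopper-Pearson) 95% intervals.** 7/20: 15.4 to 59.2%. 0/20: upper limit 16.8%. Recovery in 6/7: 42.1 to 99.6%.

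**The case against.** The plan is silent; it does not say that unrecovered patients are excluded. It allows a median, and a median can rank a minority of unrecovered patients last. The proportion recovered by discharge sits beside the time and shows how many patients lack one. At the cited rates about half of such studies would have no unrecovered patient, and the modelled gap with one is under a day. The outputs are descriptive, with no test or decision rule, and anyone given a count and a denominator can compute an exact interval.

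Most of this stands, and it sets the severity. It does not remove the point. The mean remains permitted and cannot include these patients, the ranked-last median is not specified, and the discharge proportion does not correct the time.

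Three stronger readings are tempting and are not supported.

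- A reader might infer that recovery time is understated for all AKI patients. AKI that resolved on PMB pushes the other way, and the direction can reverse.
- A reader might infer that the plan instructs exclusion. It gives no rule; exclusion follows only from what an average can contain.
- A reader might take the phrase in section 7.1.1 as an inferential safety claim. It is a statement in the Benefits section with no threshold attached. Nor is 0/20 a plausible AKI result: at 34.5% its chance is 0.655^20, about 0.02%. The example is relevant to a rarer outcome, such as a single neurotoxicity term.

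**Conclusion.** The point holds for patients with AKI present at or after PMB cessation. For them, a mean, or a median over recovered patients only, is too short whenever someone is unrecovered when data end.

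The chance of that is about 50% at the cited rates with 20 subjects, and 16 to 90% over the input ranges shown. Where it happens, the typical shortfall at 90% recovery is about 26% for the mean and 14% for the median under exponential recovery with a common discharge day. With one unrecovered among seven cases the difference is under one day; with two it is about 1.5 days (4.4 − 2.8 = 1.6 from rounded medians).

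The direction in this population follows from who is left out. The size rests on assumed distributions and on a supply-list sample size. Creatinine after discharge, if obtained, would make unrecovered patients fewer but would not supply the missing rule. The absent intervals are a small omission. Severity is minor.

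**What to change.** In section 6.3.3, drop the mean and specify the following:

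- **Population:** patients with AKI present at or after PMB cessation.
- **Estimate:** median time to recovery by Kaplan-Meier, or by cumulative incidence with death as a competing event if anyone dies. Censor unrecovered patients at the last available creatinine. Give a 95% CI where estimable, and otherwise state that the median was not reached.
- **Simpler alternative:** the median with all unrecovered patients ranked last, also reported as not reached where needed. It does not require discharge to be unrelated to recovery, so it also serves as a sensitivity analysis. When some patients leave early it can err slightly long (2.2 against a true 2.1 days in one simulated case).
- **Time origin:** state it for AKI that begins after cessation. The choice matters: if one of seven cases starts two days after cessation (an assumption), the median is 2.8 days from onset and 3.1 from cessation.
- **AKI resolved on PMB:** report the number separately and keep these patients in the denominator of the recovery proportion.
- **Proportions:** add Clopper-Pearson 95% CIs for AKI, recovery and neurotoxicity.

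The cost is a few lines of text and slightly more analysis. Serum creatinine and mortality are already collected (5.8.6, 5.8.8), so no new data are needed. The downside is that the interval for the median may be incomplete with few cases: in simulation its upper limit was not reached in 15% of sets with seven cases and 41% with five.
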